### 4.2.9.2 Missing BCVA and FST Data

If a subject stops treatment of study drug for any reason before end of trial, in general, the subject will remain in the trial and BCVA and FST data will be available and used as is in the calculations.

If a subject has no measurement within the defined visit window the value measured closest to the window will be taken.

Data will be imputed if the subject has missing BCVA and FST for any of the following reasons:

## Statistical Analysis Plan Template

Sponsor:	ProQR Therapeutics		
Protocol:	PQ-110-002		
Document Version No.:	1.0	Document Date:	04 JAN 2022

- a subject withdraws consent for unknown reasons or related to the medical procedure.
- a subject withdraws consent for reasons unrelated to the medical procedure as elicited at the end of study/early termination visit, or the subject dies from an unrelated event.

The following imputation methods will be used:

- **All-last observation carry-forward (ALL-LOCF):** All missing data of the endpoint is imputed by the respective last observation carry forward method.
- **All-baseline carry-forward (ALL-BOCF):** All missing data of the endpoint is imputed by the respective baseline value of the subject.

For the handling of missing values for the Month 12 BCVA data, two analysis will be performed as below:

- No imputation method will be used and analyze all available BCVA data.
- For the subjects with at least one ongoing AE of cataract or retinal (CME) adverse events, Month 12 assessment BCVA data will be considered as missing data and imputed using All-LOCF.

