## 2.0 INTRODUCTION

ProQR Therapeutics (ProQR) is developing an antisense oligonucleotide (AON) product, QR-110, for the treatment of patients with Leber congenital amaurosis (LCA) due to the c.2991 +1655A>G mutation (p.Cys998X or IVS26+1655A>G) in the Centrosomal Protein of 290kDa (*CEP290*) gene. Leber congenital amaurosis is a severe inherited retinal degenerative disease resulting in blindness, often in early childhood. In patients with LCA due to the p.Cys998X mutation in the *CEP290* gene (subsequently referred to as *CEP290* p.Cys998X mutation), visual symptoms are usually detectable before 1 year of age and further deterioration over time has also been reported (den Hollander 2008, Yzer 2012). Patients show severe vision disturbances from an early age and slow progressive loss of remaining vision (Cideciyan 2007, Cideciyan 2011, McAnany 2013, Jacobson 2017). There are currently no approved therapies for the treatment of LCA due to the *CEP290* p.Cys998X mutation and a large unmet medical need exists. The primary goal of the development plan for QR-110 is to provide a treatment to overcome the genetic defect in patients with at least one *CEP290* allele containing the *CEP290* p.Cys998X mutation, resulting in functional vision restoration or preservation. The intended route of administration is intravitreal (IVT) injection.

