### 4.5. Drug Exposure

The summary of exposure to study drug will be presented by treatment group for the Safety Population.

The exposure summary will summarize administration of study treatment to the first treatment eye, and the contralateral eye. The summary will include the number of doses received, the duration of treatment, the duration of follow up post first dose, the duration of follow-up post last dose, the cumulative dose, and the average daily dose, which will be calculated as follows:

- Duration of Treatment = date of last dose-date of first dose+1
- Total Duration of Follow Up Post First Dose = date of last assessment - date of first dose+1
- Duration of Follow Up Post Last Dose = date of last assessment – date of last dose+1
- Cumulative Dose = sum of all doses received
- Average Daily Dose = cumulative dose ÷ duration of follow up post first dose

The number of doses received will be summarized as a categorical variable, with the following categories, and the categories may be changed as per the available data:

- 1, 2, 3, 4, 5, 6 or 7 doses for summaries of exposure in the treatment eye
- 1, 2, 3, 4, 5, 6 or 7 doses for summaries of exposure in the contralateral eye

Listings of study drug exposure and compliance will be provided based on the Safety Population.

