### 4.8.1.3. Vision Preservation Analysis for the First Treated Eyes

A vision preservation analysis will be summarized on overall group and performed on the first treated eyes which were treated in PQ-110-001 and continue to be treated in PQ-110-002 with the following definitions of achieving the vision preservation:

- BCVA change from baseline for on-chart subjects (ie, BCVA < 1.7 logMAR based on ETDRS):
  - Among the subjects that are responders at month 12 to the -0.3 criterion
    - Remain responders at -0.3 logMAR
    - Remain responders at -0.2 logMAR (allowing a worsening of + 0.1 log MAR)
    - Have a worsening of equal or more than + 0.2 log MAR
    - Have a worsening of equal or more than + 0.3 log MAR
  - Among the subjects that are responders at month 12 to the -0.2 criterion
    - Remain responders at -0.2 logMAR
    - Have a worsening of equal or more than + 0.1 log MAR
    - Have a worsening of equal or more than + 0.2 log MAR
    - Have a worsening of equal or more than + 0.3 log MAR

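### BCVA and FST missing after withdrawal are filled by two opposing carry-forward methods with no primary named, and an analysis without imputation is stated only for Month 12 BCVA

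*SAP*

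**What the plan says.** SAP 4.2.9.2 covers missing BCVA and FST. Subjects who stop drug but stay in the trial contribute their observed values. Imputation applies to those who leave. One trigger is that "a subject withdraws consent for unknown reasons or related to the medical procedure"; the other is withdrawal for causes not connected with the procedure, or death from an unrelated cause.

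The section then states "The following imputation methods will be used" and lists two:

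- ALL-LOCF: "All missing data of the endpoint is imputed by the respective last observation carry forward method".
- ALL-BOCF: "All missing data of the endpoint is imputed by the respective baseline value of the subject".

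Neither is called primary or sensitivity, and neither has a last visit.

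Two further analyses follow, for Month 12 BCVA only. In one, "No imputation method will be used and analyze all available BCVA data". In the other, Month 12 BCVA of subjects with certain ongoing ocular adverse events is set to missing and filled by LOCF. Nothing comparable is stated for FST, or for BCVA at other visits.

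The preservation analyses of first treated eyes (4.8.1.3 for BCVA, 4.8.3 for FST) condition on Month 12 response, for example "Among the subjects that are responders at month 12 to the -0.3 criterion", and count how many keep it. They name no imputation method. Nor do the responder analyses of treated contralateral eyes in 4.8.1.2 and 4.8.3.

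**The concern.** Lasting efficacy is a secondary objective (Protocol 3.2). The study period has no fixed end (Protocol synopsis), and Protocol 2.3.1 says that dosing intervals of up to 6 months are to be explored. Whether a response lasts is therefore a main question of the extension. The Protocol introduction describes the disease as a "slow progressive loss of remaining vision", so a reading taken under treatment cannot be presumed to hold after the subject has left and dosing has ended.

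LOCF makes that presumption. In a table that asks which Month 12 responders are still responding, a carried value answers yes without an observation. Such values can only accumulate over time, so they weigh most at the late visits, where a long-term claim would be made. With no primary method and no unimputed summary at those visits, the report could lead with either of two opposite figures, and no stated table would show what was observed.

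**Working it through.** The plan is descriptive and states no power, attrition rate or expected responder rate, so there is no figure of its own to reproduce. The check applies the stated rules.

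**Inputs**
- At most 11 subjects (Protocol 5.1).
- Contralateral-eye responder thresholds: BCVA change of -0.2 or -0.3 logMAR or better for on-chart eyes (SAP 4.8.1.2); FST change of -0.5 or -0.7 log cd/m² or better (SAP 4.8.3).
- Visits every 3 months (Protocol 7.1), doses every 6 months (6.1.5), first treated eye dosed 3 months after the contralateral eye (7.2), end-of-study visit 3 months after the last dose (7.3).
- Exposure categories: "1, 2, 3, 4, 5, 6 or 7 doses for summaries of exposure in the treatment eye" (SAP 4.5), with the same categories for the contralateral eye.

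**1. Status of a departed responder**
- LOCF: the change stays at its last observed value. If that met the threshold, it meets it at every later visit.
- BOCF: change = baseline - baseline = 0. Since 0 is not ≤ -0.2, -0.3, -0.5 or -0.7, the eye is a non-responder on every numeric threshold. An off-chart eye set to its own baseline cannot change acuity category either.

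**2. Gap between the methods**

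With n eyes, R responders and d of them departed while responding, LOCF gives R/n, BOCF gives (R - d)/n and available data give (R - d)/(n - d). The LOCF-BOCF gap is d/n:

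| d | n = 11 | n = 8 |
|---|---|---|
| 1 | 9.1 points | 12.5 points |
| 2 | 18.2 points | 25.0 points |
| 3 | 27.3 points | 37.5 points |

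Illustration with assumed counts n = 11 and R = 6, exact (Clopper-Pearson) 95% intervals:

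| d | LOCF | BOCF | Available data |
|---|---|---|---|
| 1 | 6/11 = 54.5% (23.4-83.3) | 5/11 = 45.5% (16.7-76.6) | 5/10 = 50.0% (18.7-81.3) |
| 3 | 6/11 = 54.5% (23.4-83.3) | 3/11 = 27.3% (6.0-61.0) | 3/8 = 37.5% (8.5-75.5) |

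The LOCF row does not react to departures, and its interval treats carried values as observed.

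**3. Preservation rows**

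The denominator is Month 12 responders only, so each departure weighs more. Assume 6 of them, 3 leaving while responding and 1 of the 3 who stay keeping the response: available data 1/3 = 33%, LOCF (1 + 3)/6 = 67%, BOCF to a pre-treatment baseline 1/6 = 17%. In a milder case, 1 leaves and 3 of the 5 who stay keep it: 3/5 = 60%, 4/6 = 67% and 3/6 = 50%.

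**4. Possible length of carry**

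Assume seven doses in this study. For the contralateral eye the last dose is at Month 6 × (7 - 1) = 36 and the end-of-study visit at Month 39. A subject leaving after Month 12 then leaves (39 - 12)/3 = 9 later visits filled by one old value. For the first treated eye everything shifts by 3 months, giving (42 - 12)/3 = 10. Leaving after Month 6 gives 11 or 12; after Month 24, 5 or 6.

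**5. Comparison within the SAP**
- SAP 4.2.9 plans no imputation for efficacy endpoints other than mobility course, BCVA and FST.
- SAP 4.2.9.1 leaves a mobility score missing if the visit did not take place, and avoids LOCF where it would put a pre-treatment score at a post-treatment visit. For BCVA and FST, ALL-BOCF does exactly that, and no reason is given.
- SAP 4.2.9.2 also takes the value nearest the visit window, with no maximum distance. Read literally, this would act like LOCF after withdrawal and pre-empt BOCF.

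**The case against.** A reader might infer that every departed responder is counted as still responding at all later visits. The documents do not support that:

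- ALL-BOCF is listed beside ALL-LOCF with equal standing, and step 1 shows that it makes the same subject a non-responder.
- The preservation sections name no imputation method. They also concern eyes still being treated in the extension, and whether a withdrawn subject's eye belongs there at later visits is not stated.
- One might argue that BOCF also protects the response, because Baseline 002 of a first treated eye is a post-treatment value. But SAP 4.2.4 assigns Baseline 001 to first treated eyes for BCVA and FST. What remains is that 4.2.9.2 does not say which of the three baselines it means, and 4.8.1 refers to Screening without naming the study.
- The schedule of events is not in the public text and the dose categories may be changed, so the visit counts in step 4 are not a planned duration. No share of carried values can be derived.

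The stakes are also limited. The primary endpoints are adverse events, the analyses are descriptive, and individual BCVA and FST values over time will be tabulated, so a careful reader could see who stopped contributing. This lowers the risk, but it does not supply an unimputed summary or responder rate.

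Finally, available data are not neutral. Continued treatment is decided case by case on benefit and risk (Protocol 4.2), so those who remain may be those doing well. That stands, and is why the fix asks for two denominators.

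**Conclusion.** The concern holds in limited form. For BCVA and FST missing after withdrawal or unrelated death, the SAP lists two opposing single-value imputations with no primary, no stated limit on carry and no link to the responder and preservation tables. An unimputed analysis is stated only for Month 12 BCVA. Only under ALL-LOCF, and only if it feeds the preservation rows, is a departed Month 12 responder counted as still responding at each later tabulated visit.

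The firm size is at least 9.1 percentage points per departed responder between the two methods, given at most 11 subjects and BOCF from a pre-treatment baseline. The preservation examples and visit counts rest on assumed departures and timing and show direction only. The change is worth making because durability is a stated objective and the cost is small.

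**What to change.** In SAP 4.2.9.2:
- Make available data the main analysis of BCVA and FST at every visit, with the numbers observed and imputed shown per visit.
- Keep ALL-LOCF and ALL-BOCF as labelled bounding sensitivity analyses with a stated last visit.
- State that BOCF uses Baseline 001 for first treated eyes, consistent with 4.2.4.
- State that the nearest-value rule does not apply after withdrawal.

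In the preservation tables of 4.8.1.3 and 4.8.3:
- Do not count LOCF values as preserved.
- Show withdrawn Month 12 responders in a separate row for those not observed.
- Give the preserved rate twice: among those observed, and with all Month 12 responders in the denominator. The second is a worst case for those who left and should be labelled so.

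The cost is SAP wording, a few extra table rows, and a preservation rate that may look less favourable. No new data are needed.

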### 4.2.9.3 Partial and Missing Data for Adverse Events

#### 4.2.9.3.1 Partial and Missing AE Start Dates

If an AE start date is completely missing, and either the available (complete, partial) AE end date/time information indicates that the AE ended before the date/time of first dosing of study treatment on Day 1 or the subject did not receive study treatment, impute the AE start date as the date of informed consent and consider the adverse event as non-treatment-emergent.

If an AE start date is completely missing, the subject received study treatment, and either the AE end date information is completely missing or the available AE end date/time information indicates that the AE did not end before the date/time of first dosing of study treatment on Day 1, impute the AE start date to Day 1. The adverse event will be assumed to be treatment-emergent following the first dose of study treatment.

## Statistical Analysis Plan Template

Sponsor:	ProQR Therapeutics		
Protocol:	PQ-110-002		
Document Version No.:	1.0	Document Date:	04 JAN 2022

If a partial AE start date is consistent with the actual start date being on Day 1, and either the AE end date information is completely missing, or the complete or imputed AE end date/time information indicates that the AE did not end before Day 1, the imputed AE start date will be Day 1 in the following scenarios:

- The AE start time is missing (the adverse event will be flagged as treatment-emergent following the first dose of study treatment)
- The AE start time is after the date/time of first dosing of study treatment on Day 1 (the adverse event will be flagged as treatment-emergent following the first dose of study treatment)
- The AE start time is before the time of first dosing of study treatment on Day 1, and imputing the AE start date as Day 2 instead of Day 1 would be inconsistent with the partially recorded AE start date (e.g., the calendar month for Day 2 is not the same as for Day 1), or with the complete or imputed AE end date/time (in this case, the adverse event will not be flagged as treatment-emergent following the first dose of study treatment).

Otherwise, if the start date for an AE is partially recorded, the AE start date will be imputed as the date of first dose of study treatment, and the adverse event will be considered treatment emergent.

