### 4.2.9.3.2. *Partial and Missing AE End Dates*

If the end date for an AE is completely missing, the Adverse event will be assumed to be ongoing on the date of the subject's last visit. If the end date for an AE is partially recorded, then the AE end date will be re-imputed as the date of the subject's last visit.

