#### 4.7.1. Adverse Events

Adverse events will be coded using the Medical Dictionary for Regulatory Activities (MedDRA) Version 20.0 and displayed in tables and listings using System/Organ/Class (SOC) and Preferred Term.

Adverse events are summarized by subject frequencies, therefore, in any tabulation, a subject contributes only once to the count for a given adverse event (SOC or preferred term).

A treatment emergent adverse event (TEAE) is defined as an event that was not present prior to administration of the first dose of study drug and present after the first dose or if it represents the exacerbation of an event that was present prior to the first dose.

The number and percentage of subjects with any TEAE, with any TEAEs assessed by the Investigator as related to study drug and those related to drug administration (definite, probable, or possible relationship), and with any serious adverse event will be summarized by treatment group and overall. Deaths, TEAE severity, seriousness, outcomes (resolved, resolved with sequelae, not resolved, resolving, fatal and unknown) and study discontinuation due to TEAE will also be tabulated by treatment group. In these tabulations, each subject will contribute only once (i.e., the most related occurrence or the most severe occurrence) to each of the counts in the descriptive analysis, regardless of the number of episodes. No formal hypothesis-testing analysis of adverse events will be performed.

Missing or partial start and end dates will be imputed as described in Section 4.2.9.3 before determining whether an AE is treatment emergent. For subjects with an actual or imputed AE start date on Day 1, the

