## Statistical Analysis Plan Template

Sponsor:	ProQR Therapeutics		
Protocol:	PQ-110-002		
Document Version No.:	1.0	Document Date:	04 JAN 2022

AE is treatment-emergent if the AE start time was not recorded or was after the time of the first dosing of study treatment on Day 1.

An ocular TEAE following the first dose of study treatment is an ocular adverse event that was not present prior to administration of the first dose of study treatment but was present after the first dose, or an event with onset prior to the first dose with an exacerbation of the event after the first dose.

A non-ocular TEAE is a non-ocular adverse event with onset after the first dose of study treatment, or an event that was present prior to the first dose which had an exacerbation (worsening) occurring after the first dose.

If an ocular TEAE affects both eyes, it will be listed and summarized as two ocular TEAEs, affecting the first treated and contralateral eye. If a subject has multiple TEAEs which are coded to the same PT within the same SOC, that PT will only be reported once for that subject. Similarly, if a subject has multiple TEAEs which are coded to different PTs within the same SOC, that SOC will only be reported once for that subject.

In summaries of TEAEs by relationship, if there is more than one occurrence of a particular event for a subject, the event of most related will be included in the summary tables of TEAEs. In addition to presenting TEAEs by each relationship category (possibly related, probably related, and definitely related ), as indicated for the event by the Investigator, TEAEs will be summarized by the categories as being either related or not related, where an TEAE will be considered related to study treatment if the event is at least 'possibly' related (i.e., to include 'possibly related', 'probably related' and 'definitely related') or if the relationship is missing.

In summaries of TEAEs by severity, if there is more than one occurrence of a particular event for a subject, the event of greatest severity will be included in the summary tables of TEAEs. In summaries of TEAEs by both severity and relationship, the most severe of the TEAEs will be included in the summary tables of TEAEs.

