## Statistical Analysis Plan Template

Sponsor:	ProQR Therapeutics		
Protocol:	PQ-110-002		
Document Version No.:	1.0	Document Date:	04 JAN 2022

Unless otherwise stated, the following summaries of TEAEs will be presented for all non-ocular TEAEs, and separately for ocular TEAEs in the first treated eye , in the treated contralateral eye before the first dose in the study , in the treated contralaertal eye after the first dose in the study and in the non-treated contralateral eye. Unless otherwise stated, any summary of any type of TEAEs or serious adverse events (SAEs) which includes the SOC and PT of the events, will order the SOC and the PTs within the SOC in alphabetical order.

The tables that provide an overview of TEAEs will be presented by treatment group, to include the number (and percentage) of subjects who had any TEAE, SAE, TEAE leading to discontinuation from study treatment, TEAE leading to discontinuation from the trial, deaths and will summarize the number of subjects who had a TEAE by severity, by relationship to study treatment and by relationship to study treatment administration.

The adverse events that were identified by the Investigator as meeting the definition of an adverse event of special interest (AESI), as defined in Section 9.2.4 of the clinical study protocol will be supplemented by events for which an AESI has been defined but for which are not meeting the criterion for an AESI.

The following summary tables will be produced:

- Overview of Non-ocular TEAEs
- Overview of Ocular TEAEs
- Non-ocular TEAEs by, SOC and PT
- Treatment-emergent AESIs
- Non-ocular TEAEs by Severity
- Ocular TEAEs by Severity
- Non-ocular TEAEs by Relationship to Study Treatment
- Ocular TEAEs by Relationship to Study Treatment
- Non-Ocular TEAEs by Severity and Relationship to Study Treatment
- Ocular TEAEs by Severity and Relationship to Study Treatment

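### SAP 4.2.9.3.1 flags an adverse event with a partial start date and no start time as treatment-emergent even when the record places it wholly before first dose

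*SAP*

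**What the plan says.** SAP 4.2.9.3.1 sorts adverse events (AEs) with incomplete start dates into three groups.

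- **Start wholly missing.** If "the available (complete, partial) AE end date/time information indicates that the AE ended before the date/time of first dosing", the start becomes the consent date and the event is not treatment-emergent. A recorded end date, even a partial one, can therefore keep the event out of the TEAE count.
- **Partial start that could be Day 1.** The end date must also be wholly missing, "or the complete or imputed AE end date/time information indicates that the AE did not end before Day 1". With no recorded start time, the start becomes Day 1 and the event is a TEAE. The only way out is a recorded time before dosing on a record that cannot fit Day 2.
- **Every other partial start.** "Otherwise, if the start date for an AE is partially recorded, the AE start date will be imputed as the date of first dose", and the event is treated as a TEAE.

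SAP 4.2.9.3.2 sends every partial end date to the final visit; its sentence on this begins "If the end date for an AE is partially recorded, then the AE end date will be re-imputed as the date of the".

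SAP 4.7.1 defines a TEAE as an event absent before first dose and present after it, or one that worsened after it. It then says "Missing or partial start and end dates will be imputed as described in Section 4.2.9.3 before determining whether an AE is treatment emergent". For an actual or imputed Day 1 start, the "AE is treatment-emergent if the AE start time was not recorded or was after the time of the first dosing of study treatment".

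SAP 4.2.9 calls the start rule deliberately conservative, and says imputed end dates are held to the last date still credible on the record's own information.

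Ocular TEAEs are summarised separately for several eye groups, including "in the treated contralateral eye before the first dose in the study" and the same eye after that dose.

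**The concern.** For a partial start with no time, the Day 1 branch and the fallback give the same date and the same flag, so nothing else in the record can alter the classification. A record that shows an event beginning and ending before dosing becomes a TEAE. If the start month of that record were deleted, the rule for wholly missing starts would classify it correctly, so more information gives a worse answer. Nothing downstream repairs this, because SAP 4.7.1 imputes first and then accepts an untimed Day 1 start as treatment-emergent.

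The primary endpoint is the frequency and severity of ocular and non-ocular AEs (SAP 2.5.1.1), and the SAP tabulates it as TEAEs. A misclassified record therefore goes straight into a primary summary.

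**Working it through.** The plan gives no figure to reproduce. The check applies the rules literally to example records.

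Assumed for illustration: first dose on Day 1 = 15 March 2020, last visit = 15 March 2021, no start time recorded.

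| Recorded start | Recorded end | Branch reached | Start and flag under the SAP | What the record shows |
|---|---|---|---|---|
| blank | 20 Feb 2020 | wholly missing start | consent date, not TEAE | over before dose |
| Feb 2020 | 20 Feb 2020 | fallback | 15 Mar 2020, TEAE | over before dose |
| Feb 2020 | Feb 2020 | fallback | 15 Mar 2020, TEAE | over before dose |
| Mar 2020 | 10 Mar 2020 | fallback | 15 Mar 2020, TEAE | over before dose |
| 2020 | Feb 2020 | Day 1 branch | 15 Mar 2020, TEAE | over before dose |
| Feb 2020 | 20 Jul 2020 | fallback | 15 Mar 2020, TEAE | began before dose; TEAE only if it worsened |
| Mar 2020 | missing | Day 1 branch | 15 Mar 2020, TEAE | timing unknown; the flag is reasonable |

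**Start after end.** Imputed start minus recorded end:

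- Row 2: 9 days to 29 February plus 15 = 24 days.
- Row 3: at least 15 days, since the recorded end month closes on 29 February.
- Row 4: 15 − 10 = 5 days.

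**Role of the end-date rule.** In row 5, section 4.2.9.3.2 turns February 2020 into 15 March 2021. The Day 1 branch tests that imputed end and finds that the event did not end before Day 1. Repairing only the fallback would leave row 5 wrong.

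**Row 6.** Protocol 9.4.3.2 has a persistent AE that worsens entered again as a new record, so the earlier record need not be flagged to capture the worsening.

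**Where it lands.** The contralateral eye had no treatment before this study (Protocol 2.3), and its first dose is planned for Day 1 (SAP 4.2.10). There are two cases:

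- Emergence counted from that Day 1 dose: the before-dose TEAE summary is empty by definition, and the pre-dose event is wrongly added to the after-dose summary.
- Emergence counted from an earlier dose, such as one in PQ-110-001, with imputation to Day 1: the event is moved from the before-dose summary to the after-dose summary.

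**Size of one error.** At most 11 subjects enrol (Protocol 5.1). One subject is 1/11 = 9.1 percentage points of a row if all 11 contralateral eyes are treated. With 5 treated eyes (assumed), it is 1/5 = 20.0 points. Both figures assume the subject has no other event with that preferred term in the summary.

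**The case against.** **The lean is declared.** SAP 4.2.9 says start dates are meant to fall after first dose rather than in screening. The direction over-counts harm in a descriptive, open-label study with no AE hypothesis tests, and all AEs are listed. This supports the last row of the table, where timing is unknown. It does not justify overriding dates that were recorded, or creating a start after the event's own end.

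**The fallback could be read narrowly**, as covering only starts that could be Day 1. Pre-dose partial starts would then have no rule at all, and the text would still need repair. The parallel medication wording in SAP 4.2.9.4.1, where the same construction sweeps up all remaining partial dates, favours the broad reading.

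**Few records can be affected.** This stands.

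- Contralateral-eye events are captured as AEs once that eye is dosed (Protocol 9.4.1).
- Pre-existing conditions become AEs only on worsening (Protocol 9.4.3.5), and a worsening is a legitimate TEAE.
- Pre-treatment AEs are those tied to study procedures (Protocol 9.2.1).
- Screening/Day 1 should coincide with the last PQ-110-001 visit, which leaves little pre-dose window when dosing follows plan.

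**The two contralateral summaries.** A reader might infer that a pre-dose event moves between them whichever dose emergence is counted from. The documents do not support that. Under the first case above there is nothing to move from. If dosing were re-sequenced so that the first treated eye was dosed first, an imputed date at that dose would keep the event in the before-dose summary. The rule for wholly missing starts does tie first dosing to Day 1 ("ended before the date/time of first dosing of study treatment on Day 1"), which is why the two cases above are the ones to plan for.

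**Conclusion.** The concern holds as a minor correction. As written, an untimed partial start is always flagged as treatment-emergent, against the TEAE definition and the SAP's treatment of wholly missing starts. The partial-end rule departs from the principle in SAP 4.2.9 and feeds the Day 1 test.

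The effect is over-counting of TEAEs. It is zero if no such records occur, and 9.1 points on a row for one subject among 11 treated contralateral eyes. The documents do not say how many partial dates there are. A tally of possible date combinations would depend on which ones were listed and says nothing about frequency.

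Two further inferences are not supported:

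- **Month 12 BCVA.** SAP 4.2.9.2 sets these data to missing, in one of two analyses, for subjects with an ongoing cataract or CME event. A reader might suppose that an end date pushed to the last visit triggers this. The SAP does not say that ongoing status is taken from imputed dates, and investigators record an outcome for each AE (Protocol 9.3.3).
- **First treated eyes.** Events there before Day 1 already follow PQ-110-001 dosing, and Protocol 9.4.1 captures them as AEs on that basis. No misclassification is claimed.

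**What to change.** **Partial start dates (SAP 4.2.9.3.1).**

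- If the recorded start period or the recorded, unimputed end date places the event before first dose, and there is no later worsening, impute a date within the recorded period, no later than any recorded end. Do not flag the event as treatment-emergent.
- Otherwise, impute the later of the first-dose date and the first day of the recorded period.

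**Partial end dates (SAP 4.2.9.3.2).** Impute the last day of the recorded period, capped at the last visit, as SAP 4.2.9.4.2 already does for medications. In the examples, an end of February 2020 becomes 29 February 2020 instead of 15 March 2021.

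Stating which eye's and which study's dose is meant by first dose would also settle which of the two contralateral cases applies.

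The cost is a few sentences and a small programming change before database lock. No data collection changes. TEAE counts may become slightly less conservative.
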